
7. Fax Numbers
						

8. Email Addresses
						

9. Social Security Numbers
						

10. Medical Record Numbers (MRN)
						

(including record ID)						
11. Health Plan Beneficiary Numbers (including DEERS ID, Electronic Data Interchange Personal Identifier (EDIPI) or Number (EDIPN))						
12. Account Numbers						
13. Certificate /License Numbers						
14. Vehicle identifiers and serial numbers, including license plate numbers						
15. Device identifiers and serial numbers						
16. Web Universal Resource Locators (URLs)						
17. Internet Protocol (IP) address numbers						
18. Biometric identifiers, including finger and voice prints						
19. Full-face photographic images and						

any comparable images						
20. Any other unique identifying number, characteristic, or code (including non-military provider IDs)						
21. Free Text Fields						

If you are obtaining SSNs, provide a justification as to why and explain why a substitute cannot be used.

Due to guidelines stated within DoDI 1000.30, Reduction of SSN Use within DoD, the reduction or elimination of SSN usage must occur wherever possible. If SSNs are required to complete the project, the PI must provide a justification and explanation as to why a substitution cannot be used.

For example:

- If alternatives to SSN (e.g., EDIPNs or pseudo person IDs) are sufficient in other instances, will those alternatives to SSN usage be sufficient to respond to Congressional inquiries and /or Senior DoD stakeholders inquiries?
- Are alternatives to SSN used first?
- Are those alternatives to SSN insufficient to combine data from multiple data sources? Is the issue that some individuals do not possess alternatives ID numbers and SSN is the only way to identify them?

N/A

a. Will you receive or obtain health information?

Note: If you indicate you are not receiving health information, the answer must be consistent with the DHA data source. For a non-health information data request, if you are a non-MHS employee or non-MHS business associate, you may not access an information system that has PHI or LDS. For both MHS and Non-MHS employees and MHS business associates, you may **NOT** include data elements in the above table on: 1) lines 10 or 11, 2) line 21 if the free text field comes from a PHI or LDS system, and 3) lines 12, 13, or 18 if the account numbers, certificate and license numbers, biometric data, or any other data elements are health information created or received by an MHS health care provider, health plan, or business associate in relation to the physical or mental health or condition of an individual or payment for health care.

- Yes, I will receive or obtain health information
 No, I will not receive or obtain health information

b. If no data elements were checked in the above table, is it possible that the requested DHA data is or will be identifiable because of any unique data elements, triangulation, or small cell size?

- Data elements were checked in the above table, STOP HERE.

NOTE: A unique data element includes any unique features that alone are not identifiable but that could be used to identify an individual within the context of other information, such as any type of code (such as diagnosis or procedural), rank of general or admiral, gender, or race.

Triangulation means using different data elements that when combined can be used to identify an individual, such as including the above lists of unique data elements in a data set. Determining whether an individual is identifiable through triangulation requires consideration of all data elements in combination. Within the military, the use of rank and/or diagnosis code, procedural codes, or any other code that changes on a predictable basis, increases the possibility of identification. Small cell size means that there is only a small number of eligible individuals that satisfy the category description. Department of Defense Manual 6025.13, Medical Quality Assurance and Clinical Quality Management in the Military Health System MHS, provides that the threshold for de-identifying data within the MHS requires a cell size of three, but also states that the de-identification standards must meet the DoD implementation of the HIPAA Privacy Rule. Centers for Medicare and Medicaid also gives guidance on small cell size stating that no data cell less than 11 may be published or displayed. However, the Office for Civil Rights' OCR, which is the official regulatory office for the HIPAA Privacy Rule, provides that OCR does not designate a universal value for small cell size in accordance with the de-identification standard; instead, the cell size should be set at a level that is appropriate to mitigate risk of identification by the anticipated recipient of the data set. This means that a cell size of 3 or 11 may not meet the HIPAA Privacy Rule requirements if the cell size level does not appropriately mitigate risk of identification by the anticipated recipient of the data set.

Note: If dates are altered as a means of de-identifying the data, diagnosis and procedural codes need to be rolled-up or collapsed. If dates are provided "as time between events," the roll-up is not necessary.

- Yes, the DHA data will become identifiable
- No, the DHA data will not become identifiable

10.12 Do you believe it is possible for the MHS data to become identifiable because of triangulation, a small cell size, or any unique data element(s)?

Triangulation means using different data elements that are not themselves identifiable but that when combined can be used to identify an individual. For example, triangulation would use rank and race together to determine the identity of an individual with a particular health condition.

Small cell size means that there is only a small number of eligible individuals that satisfy the category description. Guidance for acceptable cell size is available from the Centers for Medicare and Medicaid Services. For example, the rank category of four star generals with a particular diagnosis may be less than 30, so the rank category may need to be expanded to include lower ranks.

A unique data element includes any unique features that are not explicitly enumerated in the categories of data in rows 1 – 20 of the table above (in Section 10.10), but that could be used to identify an individual. Unique data elements include characteristics that are not themselves identifying, such as the rank of general or admiral, or a race or gender, but within the context of other information could be identifiable.

- Yes, I believe there is a reasonable possibility the MHS data will become identifiable
- No, I believe there is no reasonable possibility the MHS data will become identifiable

10.13 Have you completed and uploaded an appropriate HIPAA document (i.e. HIPAA Authorization will be obtained or Waiver/alteration of HIPAA Authorization is being requested)?

- Yes
- No
- N/A

If yes, please check which one.

- HIPAA Authorization
- HIPAA Waiver (Full or Partial)
- Other (please provide copies when uploading Other Study Documents)

10.14 Managing Data (Data Management and/or Sharing Plan) and/or Human Biological Specimens for this Study:

Include in this section the plan for acquiring data (both electronic and hard copy), access during the study, data/specimen storage and length of time stored, shipment/transmission, and the plan for storage and final disposition at the conclusion of the study. Describe any data agreements in place for accessing data within and/or outside of your institution (e.g., Data Sharing Agreement, Data Use Agreement, Business Agreements, etc.)

Data Capture Methods:

The local study team will collect study data directly from the study participant (including in person, via mail or email, or over the phone), from their attending provider(s), clinical evaluations or, where applicable, from the participant's medical record (i.e., relevant medical and treatment history and relevant clinical notes) and record it on study Case Report Forms (CRFs). (See Appendices A-I).

The completed CRFs will serve as source documents for this study. Other source documents include relevant clinical notes, imaging, and/or test results which, if applicable, will be redacted and stored in the participant's research file.

Participants may also enter their coded data directly into REDCap using a personalized survey link (no log-in required). In these cases, the completed REDCap questionnaire(s) will be printed and added to the participant's research record as a source document.

Electronic Data Entry:

Following each research visit, a local study team member will review any completed paper CRFs for accuracy and completeness and then enter the collected non-personally identifiable data from the paper CRFs into REDCap, an encrypted, access controlled, password protected electronic data capture and management system housed on a Department of Defense (DoD) server and maintained by the Uniformed Services University Information Technology (USU IT).

Please see Appendix R for additional information on REDCap.

Ultrasound images will also be uploaded to TeleRay, more information is outlined below.

Data Storage & Access:

With the exception of the Informed Consent Form, HIPAA Authorization, Intake CRF, and electronic Master List, all research data (both paper and electronic) will be identified using a unique study ID only, and not by the participant's name, date of birth, DoD ID, or other protected identifier.

Paper research forms and source documents will be stored in a locked cabinet inside of a locked room within the Sports Medicine Clinic at Madigan.

Ultrasound images will be uploaded to TeleRay. TeleRay ensures that all accounts stored in Microsoft Azure's self-healing network with advance security protocols enabled and is only located in the USA Secure Connection: The sessions established are secure (with secured tokens that are regenerated). Random AES keys are generated by clients at the beginning of the media connection and, to increase security, additional keys are generated periodically throughout the session. TeleRay employs Transport Layer Security (TLS) to encrypt video data. The core protocols used are Secure Real-time Transport Protocol (SRTP) for media traffic encryption and Datagram Transport Layer Security (DTLS)-SRTP for key negotiation, both of which are defined by the Internet Engineering Task Force (IETF). The endpoints use Advanced Encryption Standard (AES) cipher with 256-bit keys to encrypt audio and video, and Hash-based Message Authentication Code- Secure Hash Algorithm 1 (HMAC-SHA1) to verify data integrity. No PHI/PII will be entered into TeleRay. Access to the coded data uploaded to TeleRay will be controlled and managed by the local MAMC research team.

The coded electronic research data for this study will be stored in REDCap, an encrypted, access controlled, password protected electronic data capture and management system housed on a Department of Defense (DoD) server and maintained by the Uniformed Services University Information Technology (USU IT). No PHI/PII will be entered into REDCap.

This coded electronic research data will be accessible by authorized staff from Musculoskeletal Injury Rehabilitation Research for Operational Readiness (MIRROR) which is based out of the Department of Physical Medicine & Rehabilitation (PM&R) at the Uniformed Services University (USU) and is serving as the data coordinating center for this research study. Access to the electronic coded research data will be governed strictly on an individual-by-individual basis

within REDCap. Individual data access as well as privileges will be clearly delegated, audited, and monitored by MIRROR/USU. Staff from MIRROR/USU will not have access to the paper research records or any identifiable research data.

The local study team will maintain a separate electronic master list which matches unique study IDs with participant identifying information. The electronic master list will be stored separately from the coded electronic research data in a secure, password protected document on a computer and network that requires CAC access and will only be accessible by local research staff.

All research data and forms (both paper and electronic) will only be accessible by authorized study staff, authorized staff from MIRROR/USU (coded data entered into REDCap and TeleRay only, as described above), the IRB of record, the local research office (if applicable), and applicable governmental agencies as part of their duties and in accordance with federal law. These duties include making sure that research participants are protected.

Informed Consent Forms and HIPAA Authorizations will be maintained for a period of 6 years following study closure and then securely shredded. Paper research forms will be maintained for a period of 5 years following study closure and then securely shredded. The master list connecting unique study ID to participant identifiers will be destroyed at study closure. The electronic coded research data will be maintained indefinitely as described below in protocol section 10.15.

De-identified data will be shared with Spaulding Rehabilitation Network/Massachusetts General Hospital implementing a parallel study at a civilian hospital.

Appropriate data sharing agreements in place.

Is this a data repository?

Yes No

If Yes, provide name of the Repository.

USU OCIO REDCap; TeleRay

Who will have access to the Repository?

Study investigators, study team members, and MIRROR Core team members, as appropriate.

What data type will be stored in the Repository?

- PHI
 LDS
 De-identified Data

10.15 Managing Data (Data Management and/or Sharing Plan) and/or Human Biological Specimens for Future Research:

If the study involves collecting, storing, or banking human specimens, data, or documents (either by the Investigator or through an established repository) for FUTURE research, address. How the specimens/data will be used, where and how data/specimens will be stored (including shipping procedures, storage plan, etc.), whether and how consent will be obtained, procedures that will fulfill subjects' request as stated in the consent, whether subjects may withdraw their data/specimens from storage, whether and how subjects may be recontacted for future research and given the option to decline, whether there will be genetic testing on the specimens, who will have access to the data/specimens, and the linkage, the length of time that data/specimens will be stored and conditions under which data/specimens will be destroyed.

Long Term Data Storage & Access:

The de-identified electronic dataset will be maintained by MIRROR/USU and the study team indefinitely, or as long as it is practical to maintain.

The de-identified data uploaded to TeleRay will be maintained by the local research team indefinitely, or as long as it is practical to maintain, and while funding is allotted for this service.

De-identified electronic research data will be securely transmitted from local study teams to the MIRROR /USU via REDCap, TeleRay, or the DoD SAFE application (or other comparable safe data

sharing system implemented by the local site and/or the US Army/DHA). REDCap utilizes Secure Sockets Layer (SSL) in addition to other safeguards on its web server to maintain secure communication with end-users (see Appendix R). DoD SAFE uses a TLS (Transport Layer Security) protocol when files are uploaded and downloaded. TeleRay employs Transport Layer Security (TLS) to encrypt video data. The core protocols used are SRTP for media traffic encryption and DTLS-SRTP for key negotiation, both of which are defined by the IETF. The endpoints use AES cipher with 256-bit keys to encrypt audio and video, and HMAC-SHA1 to verify data integrity.

Once received, the electronic de-identified research data will be stored within an encrypted, access controlled, password protected electronic data capture and management system housed on a Department of Defense (DoD)-compliant server.

Access to the de-identified research data will be governed strictly on an individual-by-individual basis within the secure electronic data capture and management system. Individual data access as well as privileges will be clearly delegated, audited, and monitored by MIRROR/USU. Any future research using retained data will require a research protocol to be approved by an Institutional Review Board or other authorized official responsible for protecting human subjects of research.

Any future research using retained data will require a research protocol to be approved by an Institutional Review Board or other authorized official responsible for protecting human subjects of research.

Consent for Future Use:

The Informed Consent Form for this research study states that de-identified research data will be shared with MIRROR/USU and maintained indefinitely for possible use in future research. By consenting to participate in this research study, participants agree to allow us to maintain their de-identified research data indefinitely for possible use in future research.

Participants will not be given the option to opt out of us retaining their de-identified research data indefinitely for possible future use. The consent form states, "If you do not want your deidentified data collected as part of this research study to be kept for use in future research studies, you should not sign this consent form."

Data Withdrawal from Storage:

Participants may request to have their data (including ultrasound images) withdrawn at any time before their personal identifiers have been removed. Once their data has been de-identified, it will be impossible for the researchers to locate their specific study data.

Is this a data repository?

Yes No

If Yes, provide the name of the Repository

USU OCIO REDCap; TeleRay

Who will have access to the Repository?

Study investigators, study team members, and MIRROR Core team members, as appropriate.

What data type will be stored in the Repository?

- PHI
- LDS
- De-identified Data

11.0

Statistical/Data Analysis Plan

11.1 Statistical Considerations:

List the statistical methods to be used to address the primary and secondary objectives, specific aims, and/or research hypotheses. Explain how missing data and outliers will be handled in the analysis. The analysis plan should be consistent with the study objectives. Include any subgroup analyses (e.g., gender or age group). Specify statistical methods and variables for each analysis. Describe how confounding variables will be controlled in the data analysis

Descriptive statistics will report location and scale in terms of mean and standard deviation for normally distributed variables, median and interquartile intervals for ordinal metric variables, and in terms of proportion and size for categorical variables.

Outliers will be removed if determined to be erroneous based on relevant clinical expertise. Data will be analyzed on a complete-case intention-to-treat (ITT) basis. Confounding will be principally controlled by randomization. In order to increase the precision of our estimates, we may also statistically adjust for patient demographics and relevant clinical variables if warranted based on statistical best practices.

Methods to be used for the Primary Aim: Time-to-event analyses (return to activity) will use survival analysis. All other outcome measures (including our primary outcome measure (VISA-A) and other aforementioned secondary outcome measures such as functional testing, ultrasound measures, etc.) will be analyzed using generalized additive models predicting change in each outcome measure by treatment group at 3 months. Sensitivity analyses for non-time-to-event outcome measures will be performed to evaluate trends by treatment group and will use longitudinal hierarchical/multilevel models incorporating random effects to account for repeated measures.

Methods to be used for the Secondary Aim: Due to the lack of washout period between initial and cross-over periods, as well as the removal of patient blinding (patients may choose the specific treatment they wish to receive during this final 3-month period), cross-over response will be analyzed as an exploratory aim versus an inferential aim. Due to the exploratory nature of this aim, additional or adjusted analyses may be performed to best explore and evaluate the data collected. Generalized additive models will be used to explore cross-over results and a limited set of measures will be explored (patient satisfaction, functional tests, ultrasound measures).

Multilevel models will incorporate random effects to account for repeated measures, using distribution families and link functions appropriate for the outcomes of interest, determined using QQ plots analyzed for best model fit. All statistical analyses will be performed using the R Programming language.

11.2 Sample Size:

We are requesting to enroll 160 total participants (40 per initial treatment arm) after adjusting for screen failures and attrition for a final sample of at least 112 (28 per initial treatment arm). 35 patients in each initial treatment group (140 patients total) will achieve 90% power to detect an effect size of 16 points. 30 patients in each initial treatment group (120 patients total) will achieve 90% power to detect an effect size of 17 points. 25 patients in each initial treatment group (100 patients total) will achieve 90% power to detect an effect size of 18 points. Effect size for the purpose of power calculations was defined as the difference between VISA-A at 3 months between PT only and PT + Additional Treatment (assumptions were based on PT + PBMT due to availability of comparable historical research), with statistical significance defined as $\alpha = 0.05$.

11.3 Total number of subjects requested (including records and specimens):

160

11.4 If you are recruiting by study arm, please identify the arms of the study and how many subjects will be enrolled in each arm

Across all performance sites, up to 160 participants will be randomized 1:1:1:1 to the four initial treatment arms (40 participants per arm)

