The participant will be prone with his/her feet overlying the edge of the bed with a pillow under the anterior ankle for comfort. The team member will scan initially in the longitudinal plane to identify the region of pathology near the avascular zone. The full interrogation should start at the gastroc-soleus junction and proceed distally to the Achilles insertion. Other pathology such as insertional tendinopathic changes, retrocalcaneal bursal changes, aponeurosis pathology, and Achilles tendon tears will be annotated if present. An ultrasound system capable of operating frequencies above 12 MHz will be used for the evaluation. Following the initial grey scale evaluation, color doppler with microvascular flow will be utilized in the area of interest to assess the relative level of hyperemia and neovascularity. The color doppler evaluation should be conducted in both orthogonal planes (transverse and longitudinal) at the area of maximal thickness/width. The relative level of neovascularization will be rated from grade 0: no visible vessels, grade 2: 3 to 5 vessels within the region of interest (ROI), grade 3: vessel's in up to 30% of the ROI. Following the color doppler evaluation, the elastography evaluation should be conducted in two orthogonal planes at the area of maximal thickness/width, IAW manufacture guidance on elastography image collections.

The participant will be identified on the ultrasound system using only the assigned participant ID. This information will be included on the Baseline Data Collection CRF (Appendix D). These images will also be uploaded to the TeleRay data platform. More information in Managing Data Sections 10.14-10.15.

Function: Quantitative function in heel raises to fatigue will be measured at baseline on both limbs. Ankle strength will be graded (0 to 5). We will also ask the participants to complete 20 single-leg hops on both legs and rate their pain using Defense and Veteran Pain Rating Scale (DVPRS) basic (i.e., DVPRS basic will be completed for both the right and left leg). Ankle-dorsiflexion and plantar flexion range of motion (ROM), both active and passive, will be measured using a goniometer. This information will be included on the Baseline Data Collection CRF (Appendix D).

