- The Demographics CRF (Appendix C) and the Data Collection CRF (Appendix D) will be used to obtain demographic information, Fitzpatrick Skin Phototype, and foot, ankle, and calf measurements for PBMT dosage calculation. The Fitzpatrick Skin Prototype is a rating of susceptibility to skin damage from ultraviolet (UV) radiation.
- Symptoms severity specific to Achilles will be Victorian Institute of Sports Assessment – Achilles (**VISA-A**)
 - The VISA-A is currently the only valid and reliable measure to assess function and pain in AT (validity, $P < 0.01$; test-re-test reliability, $r = 0.98$)
- Patient-Reported Outcomes Measurement Information System (**PROMIS-29**) will be used to capture other aspects of non-disease specific measures of health-related domains (physical, mental and social health).
- The University of Wisconsin Running Injury and Recovery Index (**UWRI**) will measure aspects unique to returning to running.
- Defense and Veteran's Pain Rating Scale (**DVPRS**) will capture pain; basic applied after hop test and supplemental provided at each visit.
- Lower Extremity Functional Scale (**LEFS**) will capture functional status.
- To quantify patient choice and motivation for treatment, an unvalidated survey will be obtained to determine patient goals of enrollment in study and reason for selecting a different intervention, and patient satisfaction with treatment.

Ultrasound: Ultrasound measures will be assessed at baseline, 3 months and 6 months. Measures of interest include cross-sectional area, width and degree of thickening within the tendon at site of maximal circumference and maximal pain, relative neovascularity, and elastography.

Function: Quantitative function in heel raises to fatigue, and ankle strength and ROM, will be measured at baseline, 3 months and 6 months on both limbs. We will also ask the participants to complete 20 hops and rate their pain using the Defense and Veteran's Pain Rating Scale (DVPRS).

Return to activity: We will be asking participants to record their return to activity, tracking the date, exercise and pain level and medication use using the training diary.

A chart review will be conducted at the end of 3 months to capture all PT visits.

Check-ins will be conducted to ensure at home exercise adherence and address any rehabilitation issues; weekly the DVPRS with supplemental questions will be delivered (Appendix F).

Study Visits for all treatment arms:

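### As written in section 10.1, the neovascularity scale has no correctly ordered grade for 1-2 vessels, no grade above 30% of the ROI, and overlapping grades 2 and 3

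*Combined protocol and SAP*

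**What the plan says.** The ultrasound part of section 10.1 (Baseline Data Collection) sets the scoring rule after the colour Doppler step: "grade 0: no visible vessels, grade 2: 3 to 5 vessels within the region of interest (ROI"), then "grade 3: vessel's in up to 30% of the ROI". The sentence ends there. Results are recorded on the baseline form, Appendix D, and the images are also uploaded to TeleRay.

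Section 10.2 lists the ultrasound measures without defining the scale again; neovascularity appears at the end of the list: "maximal circumference and maximal pain, relative neovascularity, and elastography". On timing it says "Ultrasound measures will be assessed at baseline, 3 months and 6 months".

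Section 11.1 places these measures among the "other aforementioned secondary outcome measures such as functional testing, ultrasound measures, etc", with VISA-A as the primary outcome. The planned analysis is "generalized additive models predicting change in each outcome measure by treatment group at 3 months". Sections 11.1 and 11.6 both specify a complete-case intention-to-treat basis. Ultrasound is also in the short list of measures to be explored after cross-over.

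**The concern.** An ordinal scale needs one grade, and only one, for each possible finding, and the grades must run in order of severity. The sentence in 10.1 skips from 0 to 2 and stops at 30% of the ROI. It also switches from a vessel count at grade 2 to a share of area at grade 3 without saying where one ends and the other begins.

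This is the operative rule for scoring, not background. The analysis uses change from baseline, so each tendon needs a valid grade at both visits. An assessor who meets a finding outside the rule must leave the item blank or improvise. A blank drops out under the complete-case rule, and an improvised grade can distort the change. Participants know their treatment, and the plan describes no blinding of the person who scans, so an undefined rule also leaves room for grading that differs between assessors or follows expectation.

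**Working it through.** No sample size, power or event figure bears on this point. The check is to map every possible finding to the grades as stated.

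**Inputs**, all from section 10.1: grade 0 = no vessels; grade 2 = 3 to 5 vessels in the ROI; grade 3 = vessels in up to 30% of the ROI.

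**Mapping**

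| Finding | Grade under the stated rule |
|---|---|
| No vessels | 0 |
| 1-2 vessels | No count grade; read literally, only grade 3 fits, above 3-5 vessels |
| 3-5 vessels | 2, and also 3 if they lie in no more than 30% of the ROI |
| 6 or more vessels, up to 30% of the ROI | 3 |
| 6 or more vessels, more than 30% of the ROI | None |

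Two of the five findings have no proper grade, and a third can take either of two.

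**Effect on the change score** (3-month grade minus baseline grade):

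- *From 3-5 vessels to 1-2.* Baseline is grade 2. At 3 months the assessor may leave a blank (change missing), keep 2 (2 - 2 = 0), round down to 0 (0 - 2 = -2) or apply grade 3 literally (3 - 2 = +1). The same reduction in vessels is recorded as missing, no change, a fall of two grades or a rise of one.
- *From more than 30% of the ROI to 30% or less, with 6 or more vessels at both visits.* There is no valid baseline grade. If it is capped at 3, the change is 3 - 3 = 0 and the reduction is lost. If it is left blank, the tendon drops out.
- *3-5 vessels within 30% of the ROI at both visits.* Both grades apply, so two assessors, or one assessor on two days, could record 3 - 2 = +1 or 2 - 3 = -1 where nothing changed.

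These are illustrations of single tendons. Turning them into a number per arm would need the distribution of vessel grades at baseline and at 3 months, and neither the protocol nor the SAP gives it.

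**The case against.** The strongest reply is that this is an unfinished sentence. Numbering that goes from 0 to 2 implies a grade 1, and Appendix D, which is not among the supplied documents, may print the full scale. A trained team member does the scanning and may use that scale in practice. This stands in part: what assessors actually do cannot be known from the text. But 10.1 would still give a different rule from the form, and the two would need to be reconciled. A grade 1 lost in typing or file conversion would explain one gap; it would not explain the overlap of grades 2 and 3 or the absence of anything above 30%.

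A second reply is that the images are kept, so a blank or doubtful grade can be redone. Sections 10.1 and 10.15 support upload to TeleRay and long retention while funding lasts. The text does not say which Doppler frames are stored, and re-grading needs a complete scale in any case.

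A third reply is that the measure matters little. It is one of several secondary ultrasound measures, section 11.6 applies a false discovery rate adjustment outside the primary outcome, and its use after cross-over is declared exploratory. All of this stands, and it limits the size of the point.

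A reader might infer something stronger: that tendons with 1-2 vessels cannot be graded at all, or that a known share of each arm is lost. The documents support neither. Read literally, grade 3 takes 1-2 vessels, in the wrong order; only findings above 30% are left without any grade. As for the share, no grade distribution is given. The planned 28 per arm in section 11.2 counts participants, whereas both limbs are scanned, so even the denominator would need an assumption.

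**Conclusion.** Wrong as written; minor, and confined to a secondary outcome. The scale in 10.1 has no correctly ordered grade for 1-2 vessels, no grade for vessels in more than 30% of the ROI, and two grades that overlap. Followed exactly, it gives missing or mis-ordered scores for tendons in those positions at baseline or follow-up. Tendons with no vessels, or with 6 or more vessels in up to 30% of the ROI, are graded without difficulty.

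The number of tendons affected cannot be computed from the documents. The conclusion rests on the current text of 10.1 being the rule in use. If the forms carry a complete scale, what remains is a protocol sentence that has to be brought into line with them. It would be wrong to infer that the trial's main comparison is compromised: the primary analysis and the power statement rest on VISA-A.

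**What to change.** 1. Replace the grading sentence in 10.1 with a complete, ordered, non-overlapping scale. It should cover 1-2 vessels and more than 30% of the ROI, and state where the vessel count gives way to the share of the ROI. The documents cite no source for the scale, so the team should name the one it intends and take the grade limits from it.
2. Reconcile that text with Appendix D and with the form used for ultrasound at 3 and 6 months. Section 10.1 names Appendix H only for the follow-up self-report battery, so the follow-up ultrasound form should be identified.
3. Where grades have already been given on the incomplete scale, re-grade the stored Doppler images, preferably by a reader who does not know the arm.
4. In 11.1 and 11.6, name a model suited to an ordinal outcome, for example a proportional-odds model of the 3-month grade adjusted for the baseline grade. The existing commitment to suitable distributions and link functions is attached to the multilevel models, not to the main 3-month analysis.

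The cost is one protocol sentence, a form check and one line in the analysis plan. No visits or measurements are added. Re-grading is the only real work, and it falls away if the forms in use already carry a complete scale.
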